1. SYNOPSIS

TITLE	Evaluation of the efficacy of the use of a Type I Collagen medical device						
	(MD-Tissue Collagen Medical Device) in the infiltrative treatment of						
	Great Trochanter Pain Syndrome. "MEDANTRO PILOT STUDY".						
STUDY DESCRIPTION	Single-centre pilot clinical investigation based on a one-samp						
	design.						
	Variables will be assessed at 6 different times: at baseline (day 0),						
	after week 1, weeks 2, weeks 6, weeks 10 and after weeks 24, i.e. 6						
	months after the start of the Clinical Investigation.						
OBJECTIVES	The objective of this study is to evaluate the efficacy of the						
	experimental treatment in terms of reduction of referred pain in						
	peritrochanteric area of the hip affected by GTPS.						
PRIMARY ENDPOINT	The primary endpoint will be assessed at week 10 and will include:						
	Assessment of the NRS score at weeks 10 compared to time						
	day 0. It can be considered clinically significant if at least 50%						
	of the treated subjects show a reduction of at least 3 points on						
	the NRS scale.						
POPULATION	A total of 49 subjects with GTPS will be enrolled.						
SELECTION CRITERIA	Inclusion criteria						
	 male and female subjects aged between 18 and 70 years; 						
	• subjects with lateral palpatory pain that has appeared for at						
	least 1 month;						
	• subjects with pain symptoms of the hip assessed according to						
	the Numerical rating scale (NRS) ≥ a 5;						
	• subjects who are able to cooperate with the assessments in						
	the investigation plan;						
	 subjects able to understand and sign the informed consent. 						
	Exclusion criteria						
	• subjects suffering from true coxalgia (with positive FADDIR)						
	 subjects suffering from ESHS (External Snap Hip Syndrome); 						
	• subjects who have already undergone candidate hip						
	replacement surgery;						
	subjects with radiological and clinical evidence of detachment						
	of the tendons of the lesser and/or middle gluteus with an						

	indication for surgical repair;				
	• subjects with evidence of radiographically documented				
	tendon calcifications;				
	• subjects with a degree of coxarthrosis of the hip that is a				
	candidate for treatment according to the Tonnis>1				
	classification				
	subjects who have taken fluoroquinolones within 30 days				
	prior to enrolment				
	subjects who have undergone treatment with hyaluronic acid				
	or corticosteroids in the hip candidate for infiltrative				
	treatment within 4 weeks prior to enrolment				
	 subjects with local or systemic infections of the candidate hip, 				
	osteomyelitis or sepsis;				
	subjects undergoing chronic treatment with corticosteroids or				
	immunosuppressants.				
	• subjects who are drug addicts, alcoholics, suffer from				
	psychiatric disorders or have clinical conditions that may				
	compromise the correct interpretation of PROMs or follow-up;				
	• subjects with coagulopathies, platelet aggregation disorders				
	or those on oral anticoagulants or antiplatelet agents that				
	cannot be discontinued during the study period				
	• pregnant and lactating subjects (female subjects of				
	childbearing age must be tested for pregnancy prior to				
	enrolment)				
	subjects with an allergy to porcine collagen.				
PHASE OF THE STUDY	Fase IV post market				
NUMBER OF CENTRES	1 Experimental Centre.				
DESCRIPTION OF THE	MD-Tissue Collagen Medical Device is an injectable medical device				
MEDICAL DEVICE UNDER	based on porcine collagen type I; the collagen content is $100\mu g/2mL$.				
STUDY					
STUDY DURATION	The total duration of the study will be 10 months. There will be a 4-				
	month subject selection and recruitment period and a 24-week				
	treatment and observation period.				
STUDY DURATION PER	The duration of the study for each subject will be in weeks 24.				
SUBJECT					
L					

2. ABBREVIATIONS LIST

AE	Adverse Event
COL-1	Collagen Type I
E-CRF	Electronic Data Collection Form
ECM	Extra Cellular Matrix
ESHS	External Snap Hip Syndrome
ESWT	Extracoroporeal Shock Wave Therapy
FADDIR	Flexion adduction internal rotation
NSAID	Non-steroidal anti-inflammatory drugs
GCP	GCP Good Clinical Practice
GTPS	Painful syndrome of the greater trochanter
ICH	International Council for Harmonisation of Technical Requirements for
	Pharmaceuticals for Human Use
mRNA	Messenger RNA
MD	Medical Device
mHHS	Modified Harris Hip Score
MMP-1	Matrix Metalloproteinase Type 1
NRS	Numerical rating scale
PRP	Platelet-rich plasma
MRI	Nuclear Magnetic Resonance
RT-PCR	Reverse transciptase-polymerase chain reaction
SAE	Serious Adverse Event
SUSAR	Suspected Serious Adverse Reaction
TIMP-1	Tissue inhibitor metalloproteinase type 1

3. INTRODUCTION

3.1 Tendinous tissue

Tendons are specialised organs that interpose themselves between muscle and bone, mediating the transmission of forces generated by muscles, thus enabling movement. They are mainly composed of specialised fibroblasts, tenocytes and extracellular matrix (ECM).

The complex microenvironment of the ECM, which surrounds and supports the cellular component of the tissue, specifically consists of three main classes of macromolecules: structural proteins (collagen and elastin), specialised proteins (fibrin and fibronectin) and proteoglycans (1).

The correct homeostasis and quantitative relationship between the cellular components of the ECM, as well as the reciprocal interaction between tenocytes and the ECM, are essential for maintaining the correct biomechanical properties of tendons (2). In fact, an alteration of the ECM may be consequent to changes in tenocyte activity, and, reciprocally, changes in the ECM may induce alterations in the tenocyte cell phenotype such as proliferation, migration and apoptosis (3)

Collagen is the main component of the tendon ECM. Although collagen type I (COL-1) is the major determinant of the tendon's biomechanical properties, comprising approximately 65-80% of its dry mass and nearly 95% of the total collagen in normal tendon (4), other types of collagen have been shown to occur in small amounts such as collagen types II, III, IV, V, VI, IX, X, XII, and XIV (Evans et al., 1998; Waggett et al., 1998, Riley, 2005).

Collagen fibres organise into bundles that form the main structural units, aligned along the length of the tendon, giving the tendon the property of resisting tensile forces. The expression of COL-I changes in relation to the tensile load applied to the tendon. The ability of collagen molecules to assemble into fibres by forming cross-links is an important requirement for the development of strength in this tissue, for stabilising the fibres themselves, and for increasing tensile strength.

The maintenance and turnover of the ECM of the tendon are therefore fundamental to the ability of this organ to resist mechanical forces and to respond to damage caused by pathological conditions (5); some authors suggest an alteration in the balance between ECM synthesis and degradation as a determinant of tendon deterioration and degeneration (3).

3.2 Greater Trochanteric Pain Syndrome

Greater Trochanteric Pain Syndrome, also known as GTPS (Greater Trochanteric Pain Syndrome) is a complex clinical condition characterised by chronic and recurrent pain in the lateral region of the hip, near the greater trochanter of the femur.

In the past, GTPS was exclusively attributed to a state of inflammation of the bursae of the peritrochanteric space, so much so that the term 'trochanteric bursitis' was confused and identified with it.

MEDANTRO" CLINICAL INVESTIGATION PLAN Version 2.5 of 08 January 2021 MDG2020711

More recently, efforts to further study the aetiopathogenesis of lateral hip pain have led to the delineation and more accurate definition of GTPS.

This syndromic condition manifests itself as the result of biomechanical and anatomo-histological alterations of the structures of the peritrochanteric space, in which, given the close anatomo-functional relationships, the origin can be traced back to three different pathological entities that can influence each other and feed the progressive exacerbation of the symptomatology. These are: external trigger hip, trochanteric bursitis and tendinopathies of the tendons of the gluteus medius and gluteus minimus muscles.

Recent studies concerning GTPS (6)(7) have shown that in most cases, this condition is due to a degenerative tendinopathy of the tendons of the gluteus minimus and gluteus medius muscles. Tendinopathy is defined as a pathological condition associated with histological changes that may result in a change in the organisation of collagen fibrils, a relative increase in the percentage of proteoglycans, glycosaminoglycans and non-collagenous components of the ECM accompanied by neovascularisation and inflammatory status (8). Tendinopathies thus lead to painful symptoms that very often also result in biomechanical functional deficits.

Clinically, GTPS presents as a pain that is often debilitating and exacerbated by activities such as walking, climbing stairs and lying on the affected side at night, associated with a progressive loss of stenia in hip abduction movements. On objective examination, there is a point of tenderness (trigger point) at the level of the greater trochanter region, which may radiate to the lumbar region and along the lateral aspect of the thigh, up to the ipsilateral knee, and a difficulty on strength versus resistance tests in hip abduction movements.

The diagnosis is predominantly clinical; a highly predictive sign is pain on trochanteric palpation ("Jump Sign"), often associated with the positive Single Leg Stance Test and the positive Ober's Test, which are secondary clinical tests aimed at identifying the aetiopathogenesis. Imaging may be used in the second instance to rule out other pathologies and confirm the diagnosis. Nuclear Magnetic Resonance Imaging (MRI) in particular can highlight the inflammatory state of peritrochanteric soft tissue. (9)

Although it is a very common syndrome(7), the treatment of painful gran trochanter syndrome, as well as that of tendinopathies in general, still represents a major obstacle because the specific cellular pathogenetic and biomechanical etiopathogenetic mechanisms are still partly unknown and many treatments are empirical (10). Traditionally, the treatment of GTPS is initially conservative and includes rest, ice, NSAIDs and physiotherapy with stretching exercises of the fascia lata (10)(11). The use of corticosteroids, with systemic or local infiltration, for the treatment of tendinopathies is highly controversial and in any case does not appear to be effective in the long term (10). Some authors have reported good results in the use of Extracoroporeal Shock Wave Therapy (ESWT) but no Level I study has been published in the literature (11). As far as biological treatments are concerned, a number of studies have been conducted in recent years with particular interest in the use of PRP (Platelet Rich

Plasma) infiltration; however, currently only one study has reported good results at 12 weeks (in terms of pain improvement and according to the mHHS, in comparison with a single corticosteroid injection) (12)(13) (16) (17) (18). In another study, promising results were reported to support the use of injected autologous tenocytes (14). Among the more invasive treatments, surgical release of the ITB and bursectomy of the trochanteric bursa appear to be indicated in particular cases. (14)

3.3 Preclinical studies

In an ex vivo study (15), the effects of MD-Tissue *Collagen Medical Device* (GUNA S.p.a. Milan, Italy) on a culture of human gluteal tenocytes were described, focusing in particular on the collagen turnover pathways, in order to understand how this medical device can influence tendon biology. MD-Tissue *Collagen Medical Device* is an injectable medical device based on porcine collagen type I; the collagen content is 100µg/2mL. Porcine collagen is similar to human collagen and highly compatible; it has a very low risk of inducing adverse effects and is therefore used in several clinical settings. In the ex vivo study, MD-Tissue *Collagen Medical Device* was used as a substrate for cell cultures of human gluteal tenocytes on culture plates. The results suggest that MD-Tissue is able to induce an anabolic phenotype in the tenocytes by stimulating their proliferation and migration; it would also be able to promote the synthesis, maturation and secretion of COL-I, thus promoting tendon homeostasis and repair. In particular, the modification of gene expression and proteins involved in collagen turnover pathways were analysed by real-time PCR, Slot blot and SDS-zymography. The data of the study showed that tenocytes cultured with MD-Tissue, compared to controls, showed increased secretion and migration of COL-1 and increased mRNA levels of the matrix metallopreotease inhibitor proteins MMP-1 and TIMP-1.

The tenocytes used for the cell cultures were gluteal tenocytes, derived from human gluteal tendon fragments (obtained from subjects without any tendon pathology, who had undergone total hip replacement surgery), which is why it is reasonable to think that the porcine collagen type I compound could be a valid treatment in GTPS. (15)

4. SCIENTIFIC REQUIREMENT

4.1 Title of the Clinical Investigation

Evaluation of the efficacy of the use of a Type I Collagen medical device (MD-Tissue *Collagen Medical Device*) in the infiltrative treatment of Great Trochanter Pain Syndrome. "MEDANTRO PILOT STUDY".

4.2 Purpose of the research

The results of the preclinical study suggest that MD-Tissue *Collagen Medical Device* can induce an anabolic phenotype in tenocytes by stimulating tenocyte proliferation and the synthesis, maturation and secretion of COL-I, thus promoting tendon repair. As these effects have been evaluated ex vivo on

tenocytes of gluteal muscle tendons, the aim of this study is to evaluate its efficacy in the local infiltrative treatment of GTPS in the peritrochanteric region, in terms of resolution of pain symptoms and recovery of abduction fatigue.

4.3 Disign clinical investigation

This pilot single-centre clinical investigation will be based on a one-sample design. Variables will be assessed at 6 different times: at baseline (T0 time), after week 1, weeks 2, weeks 6, weeks 10 and after 24 weeks the start of the Clinical Investigation.

4.4 Duration of the clinical investigation

The total duration of the study will be 10 months. There will be a 4-month subject selection and recruitment period and a 24-week treatment and observation period. (see figure 1).

[figure not shown]

Fig.1 Flow chart of the clinical Investigation

4.5 Participant population

A total of 49 GTPS subjects will be enrolled. The recruitment phase will be closed no earlier than the number of subjects envisaged in the Clinical Investigation Plan has been reached.

Only subjects will be included in the two experimental groups:

- belonging to the U.O.C. 1st Orthopaedic Clinic (Gaetano Pini Orthopaedic Institute, Milan);
- who meet the inclusion criteria and have no exclusion criteria.

4.6 Recruitment

Subjects will be enrolled after approval of the Clinical Investigation Plan by the relevant Ethics Committee of the ASST Istituto Ortopedico Gaetano Pini and notification of the study at the Ministry of Health.

Enrolment will involve subjects affected by GTPS, eligible according to the selection criteria. The diagnosis of GTPS will be made by the Principal Investigator through clinical examination and instrumental investigation of pelvis MRI for hips. The MRI examination must be recent and of good

quality; if the subject does not have one, an MRI examination will be performed prior to diagnosis and enrolment. Eligible subjects will be explained by a Co-Investigator the rationale of the Investigation Plan and the procedures involved. Consent to participate in the study will then be sought.

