4.10.2 Visit Paln

TO BASAL: Enrolment

In the course of daily clinical activity, investigators participating in the Clinical Ivestigation Plan will select subjects with GTPS. The Principal Investigator will be responsible for the correct clinical diagnosis, also making use of the instrumental examinations provided for in the Investigation Plan. Subjects meeting the inclusion and exclusion criteria will thus be identified. After having thoroughly explained the aims, purposes and procedures foreseen by the Investigation Plan, the subject will be proposed to participate in the Investigation itself. Finally, the selected subject will be asked to read the information form and to date and sign the Informed Consent and Consent to the Processing of Personal Data form.

Female subjects will have to provide evidence of a negative pregnancy test in order to be enrolled.

We will then proceed with the objective examination and the collection of the information required by the electronic Data Collection Form appropriately prepared.

This will be followed by:

- pain assessment using the NRS scale;
- assessment of pain using the Modified Harris Hip Score (mHHS) scale;
- clinical assessment of pain on palpation of the trochanter using the NRS scale;
- clinical assessment of stenia in abduction of the lower limb with the dynamometer;
- clinical assessment of phlogistic-degenerative signs by MRI of the peritrochanteric region;

The first infiltration will then be performed by means of ultrasound.

Previous or ongoing pharmacological treatments of any kind will be documented.

In order to monitor the consumption of analgesic (celecoxib 200mg / paracetamol 1000 mg) used during the investigation in the event of the onset of pain, a clinical diary will be given to the subject in which to indicate the day and the dose of drug used.

The enrolled subject will be assigned an identification code of a complex type formed by the progressive enrolment number followed by an alphanumeric code generated by GUNA S.p.a. through *Random Sequence Generator* (www.random.org.)

TO BASAL: Enrolment

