The occurrence of Adverse Events will be assessed at each visit. All Adverse Events (AEs), Serious Adverse Events (SAEs) and Suspected Serious and Unexpected Adverse Reactions (SUSARs) occurring between the date of signing the Informed Consent and the end of the Clinical Investigation will be recorded and reported.

All data collected will have to be entered by the Principal Investigator or a Co-Investigator identified by the Principal Investigator into the Electronic Data Collection Sheet provided by Guna S.p.a.

In particular, it is planned to obtain a data collection that is schematically described in the following table (Tab. 1), in which the entries to be made at each visit are shown:

PROCEDURE	VISIT	VISIT	VISIT	VISIT	VISIT	VISIT
SPERIMENTALI						
	Т 0	T 1	T 2	T 6/FU	T10/FU	T24/FU
		WEEKS	WEEKS	WEEKS	WEEKS	WEEKS
	enrolment	Visit	Visit	Control visit	Control visit	End of Clinical
	1°	2°	3°			Investigation
	infiltration	infiltration	infiltation			
Clinical diagnosis of	X					
GTPS						
Evaluation of Selection	X					
Criteria						
Signature of informed	X					
consent						
Signature of consent to	X					
personal data						

processing						
Collection of socio-	X					
demographic data						
Medical history	X					
collection						
NRS Evaluation	X			X	X	X
Assessment of pain on	X			X	X	X
palpation according to						
NRS						
mHHS assessment	X			X	X	X
Assessment of stenia in	X			X	X	X
abduction						
Evaluation of phlogistic	X					X
and degenerative signs						
on MRI						
Infiltrative Treatment	X	X	X			
Evaluation of clinical	X	X	X	X	X	X
diary						
Adverse Event	X	X	X	X	X	X
Evaluation (AE/SAE)						

Tab.1 Data collection during the Clinical Investigation Plan

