5.13 Subjects insurance

Insurance cover will be provided by GUNA S.p.a. for the entire duration of the clinical investigation project for all subjects enrolled.

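### A subject without a usable MRI is scanned to meet the Plan's own requirement before study consent is sought, and neither adverse-event capture nor the stated insurance reaches that scan

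*Combined protocol and SAP*

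**What the plan says.** Section 4.6 builds MRI into the study diagnosis: "The diagnosis of GTPS will be made by the Principal Investigator through clinical examination and instrumental investigation of pelvis MRI for hips". It asks for an up-to-date scan of adequate quality and adds that "if the subject does not have one, an MRI examination will be performed prior to diagnosis and enrolment". The next step is the explanation: "Eligible subjects will be explained by a Co-Investigator the rationale of the Investigation Plan and the procedures involved". Consent is the last step: "Consent to participate in the study will then be sought".

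Section 4.10.2 prints the T0 visit twice, in nearly the same words and in the same order. The Principal Investigator makes the diagnosis, "also making use of the instrumental examinations provided for in the Investigation Plan". Eligible subjects are identified, the study is explained, and the informed-consent and data-processing forms are signed last. The baseline assessments follow, including an assessment of inflammatory and degenerative signs on MRI. Tab. 1 begins at T0, which is also the visit of the first infiltration, and has no earlier column.

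Section 3.2 describes the diagnosis as mainly clinical and says: "Imaging may be used in the second instance to rule out other pathologies and confirm the diagnosis".

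Three provisions set the reach of subject protection:
- Section 4.10.2: adverse events "occurring between the date of signing the Informed Consent and the end of the Clinical Investigation will be recorded".
- Section 5.6: an adverse event is one in a member of the study population who has received one of the Plan's treatments.
- Section 5.13: insurance is provided "for the entire duration of the clinical investigation project for all subjects enrolled".

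**The concern.** A scan that the Plan requires, and that would not otherwise be done, is a study procedure. The Plan places it before the person has been told about the study or asked to take part. The Plan's protections are tied to the signature, to treatment or to enrolment, and all three come after the scan.

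The people most exposed are those scanned under section 4.6 who are then found ineligible or decline. They would have had a procedure for the study's sake without study consent, and they never reach the point at which event recording begins or insurance is stated to apply. Consent cannot be obtained retrospectively, so the order of steps has to be right in the Plan.

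**Working it through.** The point concerns the order of steps, so the check sets the sections side by side.

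**1. Order of steps**

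| Step | Section 4.6 | Section 4.10.2, T0 |
|---|---|---|
| MRI | Done if no usable scan exists, before diagnosis and before enrolment | Diagnosis draws on the examinations that the Plan provides for |
| Diagnosis and eligibility | Principal Investigator, from clinical examination and MRI | Principal Investigator; subjects meeting the criteria are identified |
| Explanation | Given to those already eligible | Given after eligibility |
| Consent | Sought after the explanation | Signed last, before the baseline assessments |

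The two sections agree. Neither describes a screening consent or an earlier signature.

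**2. Does the MRI item listed after consent at T0 move the scan?** No. That item is a reading of signs. The scan in 4.6 has to exist before the diagnosis, and the diagnosis precedes consent. Tab. 1 puts consent and MRI evaluation in the same T0 column and sets no order within it.

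**3. Is the scan study-driven?** Section 3.2 makes imaging optional and second-line; section 4.6 makes it mandatory and sets its own standard of recency and quality. Take a patient whose GTPS is clear clinically, or whose scan is merely too old. The only reason the documents give for a new scan is the requirement in 4.6. Section 4.14.2 also compares MRI signs at week 24 with day 0, and no other baseline acquisition is described.

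**4. Which protections reach an event at such a scan?**
- Recording window (4.10.2): opens at signature. The scan is earlier, so the event is outside.
- Definition (5.6): needs a Plan treatment. The first infiltration is at T0, after consent, so the event is outside.
- Insurance (5.13): stated for enrolled subjects. By 4.6 the scan precedes enrolment, so cover is not stated.

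Moving the signature ahead of the scan repairs only the first. Under 5.6 as written, an event at the scan would still not count as an adverse event, because no treatment has yet been given.

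**5. Size.** Let k be the number of the 49 enrolled subjects who need a scan under 4.6, and s the number scanned under 4.6 who are not enrolled. The number affected is k + s. The documents give neither term: k can lie anywhere from 0 to 49, and s has no stated limit.

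**6. Effect on the statistics.** None. The figures in 5.1 reproduce for the rule of at least 19 successes in 49:
- P(X ≥ 19 | n = 49, p = 0.25) = 0.0231; the Plan states 0.023.
- P(X ≥ 19 | n = 49, p = 0.50) = 0.9573; the Plan states 95.7%.
- The exact 95% interval for 19/49 is 25.197% to 53.761%, as stated.

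None of these depends on when consent is signed.

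**The case against.** The strongest reply is that the MRI is routine diagnostic work-up under ordinary clinical consent. Section 4.10.2 has investigators selecting subjects during everyday clinic work. Section 4.6 places the scan before diagnosis, and section 3.2 accepts imaging to confirm the diagnosis and exclude other disease. Some exclusions in 4.8, such as gluteal tendon detachment with an indication for surgical repair, are questions that a clinician would ask anyway. This stands for some subjects. It does not stand for those who are scanned only because they lack a scan that meets the standard in 4.6, and the Plan does not separate the two groups.

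A reader might infer more than the documents support:
- *That the scan is done with no consent at all.* The documents are silent on clinical consent for the scan. Only study consent is shown to come later.
- *That images are used as trial data before consent.* Acquisition can precede consent, but 4.10.2 lists the assessment of MRI signs after signature. Nothing says that scans of people who decline or fail screening enter the dataset.
- *That these subjects are uninsured.* Section 5.13 is one sentence and the policy is not part of the documents. The supportable statement is that cover before enrolment is not stated.
- *That a pregnancy test should precede the MRI.* Section 4.8 requires the test before enrolment, and 4.10.2 mentions it after the consent step. Nothing makes it a condition for the scan.

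The consent annexes and the flow chart in 4.4 were not available in the text reviewed and might address screening consent. They would still need to agree with the order given in 4.6 and 4.10.2.

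**Conclusion.** The point holds as a fault in a stated sequence. As written, a subject without a usable MRI is scanned to meet the Plan's requirement before study consent is sought. An event at that scan falls outside both the recording window and the adverse-event definition, and insurance for it is not stated.

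The conclusion rests on two assumptions: that at least some subjects would not have been scanned in routine care, which follows from setting 3.2 against 4.6, and that no screening consent exists elsewhere. The number of people affected cannot be derived from the documents. Section 5.12 commits the study to the Declaration of Helsinki and to GCP in general terms; the point does not depend on that reference. It concerns subject protection and has no bearing on the primary endpoint, its test or the sample size.

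**What to change.** 1. **Sections 4.6 and 4.10.2 (both printings of T0).** Require signed informed consent and signed data-processing consent before any MRI performed because the Plan requires it. State that scans already made in routine care remain usable.
2. **Tab. 1.** Add a screening column before T0 holding the two signatures and, where needed, the MRI, followed by the eligibility decision.
3. **Section 5.6.** Extend the adverse-event definition to events occurring after consent, including those arising from screening procedures. The recording window in 4.10.2 already starts at signature and then needs no change.
4. **Section 5.13.** State that cover starts at signature of consent, and check that the policy says the same.

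If the sponsor regards some of these scans as routine care, 4.6 should say how they are told apart from scans done for the Plan.

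The cost is one amendment to the order of steps, with matching edits to the subject information. Some subjects will sign and then fail screening; they are logged as screen failures and do not count towards the 49. The sample size and the primary analysis stay as they are.
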